5.3.2 Required Interventions

There are no required supplements or medications for this study.

5.3.3 Prohibited Interventions

As per the eligibility criteria, people utilizing the following interventions will be excluded from the study: current use of weight loss medications or supplements, such as Alli or amphetamine-based drugs that are believed to effect on weight; current enrollment in a weight loss program, such as Weight Watchers or a self-help group such as Overeaters Anonymous, or unalterable plans to enroll in one of these programs in the next year; history of or planned weight loss surgery.

5.4 Adherence Assessment

Our primary measure of adherence to study regimen is attendance at weekly class sessions, defined as 2/3 of the weekly study intervention sessions attended (i.e. 8/12).

6. STUDY PROCEDURES

6.1 Schedule of Evaluations

Assessment	Screening/ Consent Visit	Baseline Assessments	Randomization	Intervention Period	3 Month Follow-Up	Randomization to maintenance phase	6 Month Follow-Up
Informed Consent	X						
Health History	X						
Demographics and Background Information	X						
Inclusion/Exclusion Criteria	X						
Craving EMA Assessment	X	X		X	X		X
Blood Draw/Labs	X	X			X		X
Online questionnaires/sel f-report Measures		X			X		X
24-hour diet recall		X			X		X
Cognitive Measures	X				X		X
Weight		X			X		X
Enrollment/Rand omization			X				
Diet and/or Mindfulness Education				X			
Ketone monitoring for Dietary Adherence				X	X		X
Home glucose monitoring for safety				X			
Randomization to maintenance phase						X	

6.2 Description of Evaluations

6.2.1 Screening Evaluation

Consenting Procedure

At the first visit, study staff will provide participants a copy of Experimental Subjects Bill of Rights, then review the consent form with the participant. A single consent form will be used; it describes both the screening and the study procedures. If they are interested, participants will have the consent form and HIPAA form read aloud to them and will have unlimited time to review it on their own carefully. The study staff will verbally outline the important points of the consent form, including that the study is voluntary and they can drop out at any time, that participation or lack thereof will not affect their medical care, and that all information is kept confidential. The main requirements and inconveniences involved in the study will also be described. They will be informed about physical risks involved. Interested participants will then sign the consent form, the staff person will co-sign it, and a photocopy will be given to the participants to keep if desired.

Written informed consent with the participant will be done by either the Project Director, study coordinator, and/or research assistant. All staff involved in consenting will have completed human subjects CITI training. Documentation of signed consent will be completed in the study Salesforce database.

Screening

Online screener: Interested potential participants will visit the study website, which will consist of the IRB-approved study flier, with link to consent form and online screener. After completing online consent to be screened, they will complete a questionnaire to screen for initial eligibility of the following:

- T2DM, HbA1c within range, experience food cravings and craving-related eating, willing and able to participate in the interventions (including diet and mindfulness components, schedule allows for class attendance and study visits), able/willing to use own smartphone for study procedures; excluded substance abuse, mental health, medical conditions, or medications; 18 years or older, able to engage in light physical activity, English-speaking, pregnancy-related exclusions; weight-loss medications, programs, or surgery exclusions; vegan or vegetarian; unwilling to do home monitoring.

Phone screen: Study staff will review completed online screeners and call those who appear to be potentially eligible to confirm and further assess eligibility and discuss questions a participant may have.

Craving EMA: Those who pass the phone screen will be asked to complete the craving EMA screening and assessment. This step provides confirmation of food-craving and craving-related eating criterion. If this step is completed more than 4 weeks before the class start date, it will be repeated for baseline assessment prior to randomization.

In-person screening and consent visit: Those who successfully complete the above steps will come in for an in- person consent and screening visit. After completing written consent, they will complete additional screening and provide baseline data as follows:

- Demographics and background information
- Health history and medications to finalize screening for excluded substance abuse, mental health, medical conditions, or medications.
- Weight measurement and computerized tests of behavioral impulsivity and other cognitive tasks.

- Blood draw/labs to confirm eligibility: T2DM, HbA1c in range; TSH in normal range, normal liver and kidney function). If HbA1c is measured more than 4 weeks before the class start date, it will be repeated at the baseline blood draw.

All screening evaluations will be completed within 8 weeks prior to class start date.

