4. SELECTION AND ENROLLMENT OF PARTICIPANTS

4.1 Inclusion Criteria

Participants must meet all of the inclusion criteria to participate in this study:

1. History of T2DM mellitus. If taking insulin, screening labs will include C-Peptide to rule out T1DM. The study intervention is not designed for people with Type 1 diabetes who make no insulin.
2. HbA1c > 6.5% and < 12.0% at screening. The lower limit confirms the diabetes diagnosis. Persons with a HbA1c > than 12% typically need immediate attention to the medical regimen, and we aim to have this done before entering the trial to better separate the effects of improved medical regimens from the diet intervention. Potential participants with a HbA1c > 12% can be enrolled once glucose control is improved.
3. Experience food-related cravings most days of the week and eat in response to these cravings regularly. A key hypothesis is that our mindfulness approach will reduce cravings and craving-related eating, and this is primary mechanistic outcome. Thus we need to recruit participants who experience this.
4. Aged 18 years old and older. We are not enrolling younger children as they may need an intervention that is better tailored to children.
5. Able to engage in light physical activity. We will be recommending physical activity as part of the intervention.
6. Willing and able to participate in the interventions. Must be interested in following a carbohydrate- restricted diet, willing to learn about mindful eating and behavioral strategies for following prescribed diets, have sufficient control over their food intake so that they can follow either diet, and otherwise be able and willing to participate in the intervention. Intervention content must be practiced to evaluate whether it is effective.
7. Have smartphone and are willing to use it on a regular basis for data collection (e.g. craving EMA assessment).
8. Ability to speak English. Groups will be conducted in English, and we do not have the capacity, given the resources available in this proposal, to translate all course material and conduct groups into another language. We enrolled Hispanic participants into the pilot study who were fluent in English, and expect to do this in the proposed study.

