6.2.2 Enrollment, Baseline, and/or Randomization

Enrollment

Participants will become enrolled upon randomization, after meeting all screening criteria and completing all of the baseline assessment procedures.

Baseline Assessments

Those who complete the consent visit and whose screening labs are within range will complete the following baseline assessments from home/online: Qualtrics questionnaire (to assess baseline eating behavior, mood, stress, etc), 24-hour diet recall, and baseline blood draw at LabCorp convenient to them. Those whose screening Craving EMA was completed more than 4 weeks before the class start date will repeat this assessment in order to get baseline data more proximal to when the intervention starts.

Blood draws and lab tests will be done at LabCorp.

Test	Rationale	Screening	Baseline	Follow-up (3 & 6 mos)
HbA1c	Overall glucose control	x	x	x
C-peptide (for those on insulin)	Confirms T2DM in those on insulin	x		
TSH	Rule out untreated thyroid disorder	x		
Comprehensive Metabolic Panel	Rule out liver and kidney dysfunction	x		
Glucose, Plasma (fasting)*	Used to calculate HOMA-IR		x	x
Insulin*			x	x
hsCRP	Examine effects of the diet on		x	x
Lipid Panel	cardiometabolic and inflammatory		x	x
NMR LipoProfile® (Without Graph)—includes lipids	markers		x	x

24-hour dietary recall: Despite limitations of self-report measures in assessing dietary intake, they remain an important tool to assess dietary adherence. 24-hour diet recall provides a measure that complements the ketone measure by providing overall diet composition information that cannot be obtained from ketone measures. We will use the University of Minnesota's Nutrition Data System for Research (NDSR) software to perform 24-hour diet recall (<http://www.ncc.umn.edu/products/>). This is a widely-used dietary analysis program that enables the collection of multiple 24-hour diet recalls and encompasses multiple foods appropriate for diets of type 2 diabetic patients. Dietary recalls will be administered by trained dietetics volunteers by co-investigator [name], a nutrition epidemiologist with extensive history of conducting 24-hour recalls. Recalls will be entered into the NDSR software immediately after completion. Dietary recalls will be conducted without prior notification to avoid changes in diet on the reporting day.

Craving EMA: We hypothesize that a key behavior mechanism by which training in mindfulness can

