improve diet adherence is through reducing eating behavior in response to food cravings. This mobile, real-time EMA approach allows us to capture eating-related behavior and that is often brief and automatic and therefore poorly suited to traditional retrospective questionnaires. Participants will complete EMA of food cravings and craving-related eating via smartphones prior to, during, and following the intervention, a total of up to 6 times. During each of these craving-assessment periods, participants will receive mobile cravings assessment via text 3 times per day for 3 days. The text message will ask them to complete a short questionnaire regarding whether they have experienced any food-related cravings in the past few hours, whether they have eaten in response to these cravings, and what they ate. They will also be asked to rate their stress level during the day.

Computerized Cognitive Measures: The computer session will comprise approximately 20-30 minutes of the tasks described below. These tasks can be adjusted to be shorter than their stated length by reducing the number of trials administered. This is a common practice in neuropsychological science research. We will create a 20-30 minute battery from the following tasks:

- Delayed Discounting³⁷; The DD (1 minute) assesses the extent to which individuals value delayed versus proximal rewards. Individuals who discount delayed rewards at a high rate are more likely to engage in substance abuse, overeating, or problem gambling. This 5-trial adaptation of the original Delayed Discounting,³⁸ task has been validated and is an effective way to assess discount rates while reducing participant burden. The primary outcome is the participant's point of indifference, which is computed with intertemporal choice tasks that present a series of discrete choices between a larger quantity of a reward that is delayed and a smaller amount of that commodity that is available immediately.

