9.2 Sample Size and Randomization

Target sample size: 180; 60 participants in the first/R61 phase. 120 in the second/R33 phase.

Our primary hypothesized mechanism is change in frequency of eating in response to cravings. Based on preliminary data, we expect that participants will report that on average, they have eaten in response to cravings on 50% of days on EMA measures at baseline (SD 11%). Our key concern is whether the Ed+MBI group has a significant decrease in days of eating in response to cravings. With N=30 persons in each arm, we will be able to detect a statistically significant decrease with 80% power (alpha=.05), if the group experiences eating in response to cravings on 44% of days or less. We will also test whether there are differences in decreases in cravings between groups.

Based on typical diet interventions for obese persons, we estimate that this will decrease to 30% of days in the Ed group, and 20% of days in the Ed+MBI group, for a mean difference of 10% (SD of 11%). With 30 people in each arm, this will provide us with a power of 80% to detect a statistically significant difference, using a two-tailed test, alpha=.05. For this phase, in which we are screening for evidence of effect on the proposed mechanism, we believe that a one-sided test, corresponding the hypothesis that the Ed+MBI group will have a greater effect on craving related eating than Ed alone, we will have 88% power. Note that we are not accounting for potential drop-outs in the analysis. We

anticipate that almost everyone will get through at least 4 weeks of intervention, which will provide initial data that can be used on all participants. In our pilot study of persons with T2DM and carbohydrate restricted diets, 94% completed the full 13 session program. Even if there is 20% dropout with no usable data, we will have 80% power to detect a statistically significant difference between groups in craving related eating, using a one-sided test.

Though of lesser concern at this early stage, we aim to test whether our hypothesized mechanisms are correlated with dietary adherence measures and will use linear regression. Using our overall sample of N=60, we will have greater than 80% power to detect a significant correlation if the true correlation coefficient (r) is .43 or greater. If we look just at the Ed+MBI group, we will have 80% power to detect a significant correlation if the true correlation coefficient (r) is .53 or greater.

Treatment Assignment Procedures

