For each of these measures, our primary analysis will be comparison of changes from baseline to follow-up time points between groups (see overall analysis approach above). We will also assess changes from baseline to follow-up within each group to help assess the potential effect of each intervention arm on these measures. We will also test for preliminary evidence that each of these proposed mechanisms is associated with dietary adherence. Dietary adherence will be measured two ways: (1) proportion of blood ketone measures $\geq 0.3\text{mmol/L}$; (2) proportion of kcal from carbohydrate, using 24-hour diet recall. Each of our mechanism measures are continuous variables. We will therefore assess correlations between each of the mechanism measures and the dietary adherence measures, using linear regression. Finally, we will perform initial analysis of whether there are differences in two important clinical outcomes between intervention groups: HbA1c (to examine glycemic control) and weight. These clinical outcomes should result from our intermediate behavioral outcome of improved dietary adherence. We do not expect to have adequate sample-size in either phase of this study to address this question, but believe that preliminary assessment of these outcomes should be performed in case there are dramatic differences between groups even with limited sample size.

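### The EMA burst that qualifies late-screened participants also serves as their primary-outcome baseline, so regression to the mean can create a spurious within-arm decrease (the between-arm comparison is not biased)

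*Combined protocol and SAP*

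**What the plan says.** Section 4.1 requires candidates to "Experience food-related cravings most days of the week and eat in response to these cravings regularly". The screening EMA tests this. Section 6.2.1 says "This step provides confirmation of food-craving and craving-related eating criterion", and Section 4.3 lets only those who get through the screening steps come to the consent visit.

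Section 6.2.1 then sets the repeat rule: "If this step is completed more than 4 weeks before the class start date, it will be repeated for baseline assessment prior to randomization". Section 6.2.2 repeats it: "Those whose screening Craving EMA was completed more than 4 weeks before the class start date will repeat this assessment". The reason given there is to have baseline data closer to the start of the intervention. The list of baseline tasks for all participants in 6.2.2 does not include the EMA.

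In each assessment period "participants will receive mobile cravings assessment via text 3 times per day for 3 days". Bursts occur "prior to, during, and following the intervention, a total of up to 6 times". Section 9.5.1 names five outcome time points: baseline and weeks 7, 13, 19 and 26.

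The schedule in Section 6.1 marks the craving EMA under both Screening and Baseline, with no condition.

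Section 9.2 makes a significant fall within Ed+MBI its main question, and states 80% power "if the group experiences eating in response to cravings on 44% of days or less", from 50% at baseline. Section 9.6 makes the between-group comparison of changes primary and adds: "We will also assess changes from baseline to follow-up within each group to help assess the potential effect of each intervention arm".

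**The concern.** One short, noisy measurement does two jobs for part of the sample: it decides who enters, and it is the value from which change is measured. People who pass a threshold on three days include some who had an unusually bad three days. Their next burst is lower on average even if nothing has changed. The 4-week rule deals with the age of the burst and not with the selection.

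What is at stake is the within-arm result. The R61 phase looks for preliminary evidence that the mindfulness components move the mechanism, and the plan counts a pre/post fall in Ed+MBI towards that. Some or all of such a fall could come from the entry rule. The baseline variable also mixes two kinds of measurement, selected and unselected, according to when a person was screened.

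**Working it through.** **1. Is the screening burst really reused?** The documents never say so in one sentence, but the parts fit. The repeat is conditional in two sections, and its stated purpose is a more recent baseline. The EMA is missing from the baseline tasks for everyone. Five outcome time points against a maximum of six bursts leave the sixth for those who repeat. Only the Section 6.1 table, read literally, points the other way.

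**2. The plan's own within-arm figure.** Inputs from 9.2: n = 30, SD 11 points, alpha 0.05 (taken as two-sided; 9.2 does not say), power 80%.
- Normal approximation: 11 × (1.960 + 0.842)/√30 = 5.6 points. Noncentral t: 5.8 points.
- 50 − 5.8 = 44.2, which rounds to the stated 44%. The figure reproduces if the SD of change is 11.

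**3. Size of the regression effect, scored in days.** Not in the documents, so assumed: the cut-off (eating in response to cravings on at least 1, or at least 2, of 3 days), the between-person SD of the true rate (11, 20 or 30 points), a true mean of 50% among those reaching the EMA, and no real change. Let p follow a beta distribution and X, the number of days, be binomial(3, p). The effect is E[X/3 | X ≥ k] − E[p | X ≥ k].

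For SD 11:
- a + b = 0.25/0.0121 − 1 = 19.66, so a = b = 9.83.
- P(X = 0) = (9.83 × 10.83 × 11.83)/(19.66 × 20.66 × 21.66) = 0.143.
- At least 1 day: the qualifying burst averages 0.5/0.857 = 58.4%. The same people's true rate is (0.5 − 0.143 × 9.83/22.66)/0.857 = 51.1%. The difference is 7.2 points.
- At least 2 days: the burst averages (0.143 + 0.357 × 2/3)/0.5 = 76.2%. The true rate is 53.5%. The difference is 22.7 points.

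**4. Share reused.** Screening runs from 8 weeks before class start (6.2.1) and randomisation is at about 2 weeks (6.2.2). Reuse covers weeks 4 to 2. If bursts are spread evenly (assumption), the share is (4 − 2)/(8 − 2) = 1/3.

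**5. Result at one third reused, true mean 50%.** The false-positive rate is the simulated chance of a significant decrease in one arm of 30 (paired t-test, no true change, nominal 2.5% in that direction).

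| Cut-off | True SD | Effect, all reused | Effect, one third reused | False-positive rate |
|---|---|---|---|---|
| ≥1 of 3 days | 11 | 7.2 | 2.4 | about 5% |
| ≥1 of 3 days | 20 | 7.2 | 2.4 | about 5% |
| ≥1 of 3 days | 30 | 6.5 | 2.2 | 5–6% |
| ≥2 of 3 days | 11 | 22.7 | 7.6 | 17–18% |
| ≥2 of 3 days | 20 | 18.5 | 6.2 | 14% |
| ≥2 of 3 days | 30 | 12.7 | 4.2 | 10% |

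With a fresh baseline for everyone the expected change is about 0 and the rate returns to about 2.5%.

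**6. Higher true mean.** At 60% to 70% and one third reused, the effect is 0.8 to 1.6 points (≥1 day; rate about 3% to 5%) or 2.1 to 5.5 points (≥2 days; about 6% to 12%).

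**7. On the plan's own scale.** Take the observed SD of 11 and cut off the lowest fraction q of a normal distribution with reliability ρ. The effect is 11 × (1 − ρ) × φ(z_q)/(1 − q).
- q = 10%, ρ = 0.7: 11 × 0.3 × 0.195 = 0.6 points.
- q = 50%, ρ = 0.3: 11 × 0.7 × 0.798 = 6.1 points.

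These assume full reuse. One third reused gives 0.2 to 2.0 points.

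**8. Between arms.** In every setting the simulated mean difference between arms is about 0 and the two-sided type I error is 4.2% to 5.7%.

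**The case against.** The strongest reply is that the primary analysis is randomised. Both arms pass the same gate and are allocated after baseline, so the regression effect cancels in expectation. This stands. A reader might infer that the reuse can mimic a benefit of Ed+MBI over Ed. It cannot, and step 8 shows none.

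A reader might also infer that a truncated baseline costs precision between arms. For the planned change scores it does not. With true SD 11 and full reuse, the SD of change falls from 39.9 to 36.6 points (≥1 day) and from 39.8 to 32.7 (≥2 days). No loss of precision is claimed.

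The size can fairly be challenged too. No cut-off is stated, and a rule of two days of eating is only one reading of a criterion that speaks of regular eating. Candidates have already passed online and phone screens, so their true rate may exceed 50%. Full reuse is an extreme, given the short window before randomisation. It gives false-positive rates of about 18% to 19% (≥1 day) and 61% to 97% (≥2 days), but the documents do not support treating these as expected values.

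Finally, the day-count model implies an SD of change of about 33 to 40 points at these shares and a mean of 50%, against the 11 behind the 6-point target. Setting its point falls directly against 6 points mixes scales. The false-positive rates avoid this, because effect and SD come from the same model. On the plan's scale, 6.1 points is the top of the range and needs full reuse.

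**Conclusion.** The concern holds for the within-arm pre/post analyses only. For participants screened within 4 weeks of class start, the text makes the qualifying burst the baseline, and the resulting regression to the mean can account for part or all of an observed fall in Ed+MBI.

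At a true mean of 50% and one third reused, the spurious fall is roughly 2.4 points (≥1 of 3 days; false-positive rate about 5%) or 4 to 8 points (≥2 of 3; about 10% to 18%), against a nominal 2.5%. A lenient cut-off or a higher true mean makes it smaller. With SD 11 and simple truncation it is 0.6 to 6.1 points under full reuse. The cut-off, the reused share and the true-rate distribution are all assumptions, so the direction is firm and the size is not. If the Section 6.1 table is what is done in practice, and the Baseline burst is the one analysed, the problem disappears. The documents need to say which applies.

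**What to change.** In 6.2.1 and 6.2.2, replace the 4-week condition: every participant completes a new 3-day EMA burst after eligibility is confirmed and before randomisation. State in 9.5.1 and 9.6 that only this burst is the baseline and that the qualifying burst is never used as an outcome value. This also brings the text into line with the schedule in 6.1.

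Screening, baseline and weeks 7, 13, 19 and 26 make six bursts, within the stated maximum. Participants screened early already follow this pattern. The cost is a wording change, three more days of text prompts for late-screened candidates and a slightly tighter run-up to randomisation. No visit is added.
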